6.1.5 Recommended Phase II Dose (RP2D)

The RP2D of APR-246 will be defined as the dose at which <2 out of 6 patients experience DLT during the 4-week safety assessment period after administration of APR-246 in combination with venetoclax and/or azacitidine.

DRT consisting of the Medical Monitor, Site Principal Investigators, and other clinical research personnel that the Sponsor may deem appropriate, will hold DRM on an interim basis at a frequency dependent on study accrual. At these meetings, the DRT will review AEs and DLTs and make recommendations regarding the RP2D. In the expansion portion of the study, the DRT will evaluate safety and tolerability after 5 patients have completed 1 cycle of treatment in each cohort. All accumulated safety data will be discussed during DRMs.

6.2 Dose Interruptions/Withholding

Study treatment may be withheld from a patient based on the Investigator's decision in the event of intercurrent illness, AE, administrative reasons, or other reasons. If the patient's condition subsequently improves, or the situation that resulted in withholding study drug rectifies itself, the Investigator may resume dosing as soon as possible, unless the delay is more than 4 weeks.

Dosing should be delayed for any DLT-equivalent toxicity and possible NCI CTCAE > Grade 2 AEs considered related to study medication. At the Investigator's discretion, dosing may recommence when the toxicity has resolved to Grade 2 or less. Immune-related reactions or allergy should resolve to \leq Grade 1.

Treatment will be discontinued if a TEAE has not resolved (to acceptable grade) after \leq 4 weeks.

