6.1.4 Dose-Limiting Toxicity

An event will be considered a DLT per NCI CTCAE version 5.0 criteria if it occurs within 4-week safety assessment period (Cycle 1 of study treatment) and meets at least one of the criteria below:

- Absolute neutrophil count (ANC) not recovering to $>0.5 \times 10^9/L$ and/or platelets not recovering to $>25 \times 10^9/L$ by day 42 of study treatment in the absence of active leukemia/myelodysplasia;
- Grade ≥ 3 nausea/vomiting/diarrhea or CNS toxicity that does not resolve to Grade ≤ 1 within 7 days despite treatment interruption and maximum medical therapy;
- Treatment-related non-hematological Grade ≥ 3 toxicity that does not resolve to Grade ≤ 1 .

A DLT will be considered related to the study treatment unless there is a clear, alternative explanation for the AE. A \geq Grade 3 metabolic or electrolyte abnormalities that is not clinically significant and is adequately controlled within 72 hours is not to be considered DLT. A tumor lysis syndrome that responds to therapy and resolves within 72 hours is not to be considered DLT.

Additionally, AEs that meet the above criteria, but occur after the DLT evaluation period will not be defined as DLTs, but will be reported as AEs/Serious Adverse Events (SAEs) and will be reviewed across all cohorts during the study to help determine the AE profile. A patient

that discontinues therapy during Cycle 1 without DLT is considered evaluable for the purpose of safety only if at least 80% of doses of APR-246 in combination with venetoclax with and without azacitidine were administered in the first cycle.

Patients who are tolerating APR-246 in combination with venetoclax and/or azacitidine, will not have to discontinue dosing prematurely due to the occurrence of DLTs in another patient in the same cohort, unless decided by the DRT. If requested by the Investigator, depending on the nature of the DLT and patient status, the DRT and the Sponsor may allow a patient to continue with study treatment at a reduced dose.

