6.3.2 Management of CNS Adverse Events

If a patient reports any clinical AE of any grade during the administration period of APR-246 that could be considered to originate from the CNS (e.g. dizziness, vertigo, nausea) then the patient will be given a rescue medication as per the institutional standard of care.

Dose modifications of APR-246 have been successfully used to manage potential CNS effects occurring during the infusion (Table 4). For any clinical AE Grade ≥ 3 , the infusion of APR-246 should immediately be stopped, and if all symptoms resolve to CTCAE \leq Grade 1 within 2 hours, the infusion of APR-246 may be resumed at the same infusion rate. If the same symptoms do occur or increase in severity during re-challenge the infusion of APR-246 should be stopped.

If the event lasts longer than 2 hours, then the APR-246 infusion should be discontinued for that day, the remaining drug should be discarded.

Table 4. Management of CNS Adverse Events (Dizziness, Dyskinesia and Ataxia)

Worst toxicity	Dose Modifications for APR-246
Grade 1	Maintain dose level
Grade 2	If resolved to \leq Grade 1 with medical therapy, continue same dose level If not resolved despite treatment interruption and maximal medical therapy, stop infusion and \downarrow 1 dose level for subsequent dose
Grade \geq 3	Stop infusion and give medical therapy. If resolved (to \leq Grade 1) with medical therapy, infusion may continue at the Investigator's discretion. \downarrow 1 dose level for subsequent dose
Grade 4	Permanently discontinue patient from APR-246.

In prior studies, prochlorperazine 10 mg orally tid (three times daily) has been reported to be an effective treatment that may also be used prophylactically. When prochlorperazine is used prophylactically, start the day prior to the Day 1 and continue 10 mg tid to day 4 (as needed). The US label for prochlorperazine does not list QT interval prolongation as a known risk associated with use of this drug.

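### Sections 6.1.4 and 6.2 give different rules for restarting treatment after a Cycle 1 DLT (who authorises it, and whether the dose is reduced), and neither says which prevails

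*Combined protocol and SAP*

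**What the plan says.** Three places in the protocol govern what happens after a severe toxicity.

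- **Section 6.1.4 (Dose-Limiting Toxicity).** If the Investigator asks, and depending on the nature of the DLT and the patient's status, "the DRT and the Sponsor may allow a patient to continue with study treatment at a reduced dose".
- **Section 6.2 (Dose Interruptions/Withholding).** The trigger is: "Dosing should be delayed for any DLT-equivalent toxicity and possible NCI CTCAE > Grade 2 AEs considered related to study medication". The restart rule follows: "At the Investigator's discretion, dosing may recommence when the toxicity has resolved to Grade 2 or less". A stricter threshold, Grade 1 or less, is given for immune-related reactions and allergy. The DRT, the Sponsor and the restart dose are not mentioned.
- **Section 6.3.2, Table 4 (CNS events).** For an event of Grade 3 or above that has come down to Grade 1 or less "with medical therapy, infusion may continue at the Investigator's discretion", and the subsequent dose goes down one level. A separate Grade 4 row ends APR-246 permanently. No DRT or Sponsor step appears.

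**The concern.** Sections 6.1.4 and 6.2 appear to answer the same question for the same patient in different ways. Under one, the Investigator asks and others agree, and the patient continues at a reduced dose. Under the other, the Investigator decides alone and the dose is left open. A site that reads only 6.2 can restart a patient after a DLT without the review that 6.1.4 describes, and would be following the protocol as written there.

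The first thing at stake is patient safety. The second is comparability of exposure: adverse events after a restart depend on the dose given and on whether anyone outside the site reviewed the case. Both could vary by site for reasons that have nothing to do with the patient.

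**Working it through.** No arithmetic applies, and the plan gives no figure on this point to reproduce. The check is a comparison of the texts.

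| | 6.1.4 | 6.2 | Table 4 (6.3.2) |
|---|---|---|---|
| Event | DLT, tied to Cycle 1 | DLT-equivalent toxicity, or related AE above Grade 2 | CNS event, Grade 3 or above (Grade 4 has its own row) |
| Who decides | Investigator asks; DRT and Sponsor may agree | Investigator | Investigator, on continuing the infusion |
| Grade required | None stated | 2 or less (1 or less if immune-related or allergic) | 1 or less, to continue the infusion |
| Dose | Reduced; drug and size not stated | Not stated | One APR-246 level down for the subsequent dose |

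**Step 1. Do 6.1.4 and 6.2 cover the same patients?** Section 6.2 opens with "Dosing should be delayed for any DLT-equivalent toxicity", a term the protocol does not define. It could mean only late events, since 6.1.4 says that events meeting the criteria after the evaluation period "will not be defined as DLTs, but will be reported as AEs/Serious Adverse Events (SAEs". The overlap does not depend on that reading. Both non-haematological DLT criteria require Grade 3 or higher, and 6.1.4 adds: "A DLT will be considered related to the study treatment unless there is a clear, alternative explanation for the AE". A related non-haematological DLT is therefore a related event above Grade 2 and falls under the second part of the 6.2 trigger. The haematological criterion is written in cell counts and not in grades, so this argument is made for the non-haematological criteria only.

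**Step 2. Can a DLT meet the 6.2 restart threshold?** Yes. The third DLT criterion is a treatment-related non-haematological "toxicity that does not resolve to Grade" 1 or less, from a starting grade of 3 or higher. The nausea/vomiting/diarrhoea and CNS criterion is similar, with a 7-day limit. An event that falls from Grade 3 to Grade 2 and stays there can count as a DLT under 6.1.4 and also satisfy the threshold in 6.2. Both rules then apply to that patient.

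**Step 3. Does either section yield to the other?** No. Neither 6.1.4 nor 6.2 cites the other or states an order of precedence. Sections 6.3.5 and 6.3.6 send sites to 6.2 for guidance on APR-246 dose modification, so 6.2 is a place where sites will look.

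**Step 4. Which results can it touch?**

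- A DLT is counted when the event meets the definition, before any restart decision. The DLT count and the RP2D rule (fewer than 2 of 6 patients with a DLT) do not depend on the restart rule.
- The Synopsis reports no DLTs in the 6 patients reviewed in each lead-in cohort, 6 + 6 = 12 in all, so no restart after a DLT arose among them.
- The expansion remains open to it. Section 6.1.4 ties DLTs to Cycle 1 without restricting them to the lead-in, and the DLT-evaluable population in Section 9.2 is not restricted either. About 70 patients are planned in up to five cohorts. Expansion Cohort 5 (APR-246 with azacitidine) has no lead-in cohort for that combination in Table 3.

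**The case against.** The best defence is that both rules are permissive and can be met together: a site can wait for the 6.2 grade, ask the DRT and the Sponsor, and use a reduced dose. On that view 6.1.4 is the specific rule, 6.2 is the general one, and only a cross-reference is missing. The protocol does layer specific rules over 6.2 elsewhere, for QTc and for CNS events. This has some force, but it does not dispose of the point. Section 6.2 names DLT-equivalent toxicity expressly and gives the decision to the Investigator, so a reader cannot tell that it was meant to yield.

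Several stronger readings are tempting, and the documents do not support them.

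- *Section 6.2 directs a full-dose restart.* It does not. It is silent on dose, and Section 6.1.1 allows the APR-246 dose to be reduced for toxicity the patient cannot tolerate. That reduction is optional and not tied to restart, so the difference from 6.1.4 remains.
- *The Grade 1 and Grade 2 limits contradict each other.* They serve different functions: one classifies an event as a DLT, the other permits restart. Their difference matters only because it places some patients under both rules.
- *Table 4 requires Grade 1 or less before any later dose.* Its Grade 1 condition concerns continuing the infusion in progress. For an unresolved Grade 2 event it moves to a lower level for the subsequent dose without requiring Grade 1 first.
- *The discrepancy is worth 11% of dose.* That is (4.5 − 4.0)/4.5 = 11%, or 18 versus 16 g over four days. It assumes one APR-246 level under 6.1.4 and full dose under 6.2. Neither is stated.
- *The RP2D is in doubt.* It is not, for the reasons in Step 4 of the working.

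**Conclusion.** The inconsistency holds in a limited form. For a related non-haematological Cycle 1 DLT, 6.1.4 and 6.2 differ on who authorises restart and on whether a reduction applies, and the protocol does not say which governs. Table 4 adds a separate CNS rule that is not tied to either. This is a conflict between stated rules and more than a missing detail.

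Its size cannot be put as a number. The documents do not say how many expansion patients will have a Cycle 1 DLT, and the lead-in suggests there may be few, though 0 of 12 does not exclude them. Any effect would fall on patient safety and on adverse-event frequencies after restart, which contribute to the primary safety endpoint in Section 9.3.1.

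The conclusion rests on two readings: that the DLT definition and restart provision in 6.1.4 apply in the expansion cohorts, which the text does not restrict, and that a DLT presumed related under 6.1.4 counts as related for 6.2. It does not depend on how DLT-equivalent is understood. The point should be corrected while expansion patients can still be affected.

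**What to change.** The sponsor's clinical team should reconcile Sections 6.1.4, 6.2 and 6.3.2 with Table 4. The result should be one restart rule for a DLT or DLT-equivalent event that states:

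- who authorises the restart;
- what resolution grade applies;
- whether a dose reduction applies and, if so, to which drug;
- what DLT-equivalent means, and how the CNS rule fits in.

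Each section should then refer to that rule. Which rule stands is a clinical decision for the sponsor, and none is proposed here.

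Optionally, add a flag to the safety listings for patients redosed after a DLT or DLT-equivalent event, with the dose given. Section 9.4 already summarises adverse events leading to dose modification, so this adds only the link between the event, the restart and the dose.

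The cost is wording in one amendment and, if adopted, one derived variable. No extra patients, visits or procedures are needed.

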6.3 Supportive Management

6.3.1 APR-246

This section outlines the requirements for proceeding with treatment with APR-246, and the protocol rules for APR-246 dose modification due to toxicity.

At screening, 12-lead ECGs should be collected in triplicate to confirm QT interval does not exceed 470 msec in patients without pre-existing bundle branch block (BBB) and/or pacemaker. For patients with pre-existing BBB and/or pacemaker, QTcF at screening should not exceed baseline reading known per medical history. QT interval must be calculated from a mean of all three ECG readings using Fridericia's correction ($QTcF = QT/RR^{0.33}$).

During Cycle 1 ECG should be collected in triplicate prior to infusion of APR-246 and at the end of infusion (EOI) of APR-246 (6 hours after start of infusion, ± 30 min) on Days 1–4. QTcF must be calculated from a mean of all three ECG readings to confirm it does not exceed 470 msec in patients without pre-existing BBB and/or pacemaker. For patients with pre-existing BBB and/or pacemaker, QTcF measurements in Cycle 1 should be at or below values recorded during screening period.

If a pre-dose ECG shows $QTcF \geq 470$ msec, the QTc reading should be confirmed by manual assessment using Fridericia's correction ($QTcF = QT/RR^{0.33}$). Serum concentrations of electrolytes should be monitored and corrected, if necessary. Additionally, concomitant medication should be reviewed and adjusted, if necessary. ECG may be repeated at any time, including the same day. APR-246 may only be administered when QTcF has returned to <470 msec. If APR-246 is given on the same day, procedures outlined in the Schedule of Study Evaluations ([Table 8](#)) must be followed. If APR-246 cannot be administered on the same day, that dose must be omitted from the cycle.

If there is a significant change in QTcF, defined as either: a) increase >60 msec from baseline (or pre-dose), or b) increase to an absolute value ≥ 501 msec, i.e. consistent with NCI CTCAE Grade 3 QTc prolongation, QTc prolongation must be confirmed by a manual assessment of the ECG, and using Fridericia's correction ($QTcF = QT/RR^{0.33}$). If confirmed, the APR-246 therapy should be interrupted until a cause (electrolyte disorders or an effect of a concomitant medication) has been identified and addressed, and QTcF has returned to <470 msec. If all other causes for clinically significant QT interval prolongation are excluded, APR-246 must be permanently discontinued.

During subsequent cycles ECG should be collected in triplicate prior to infusion of APR-246 on Day 1 of each cycle. QTcF must be calculated from a mean of all three ECG readings to confirm it does not exceed 449 msec in patients without pre-existing BBB and/or pacemaker. For patients with pre-existing BBB and/or pacemaker, QTcF measurements in subsequent cycles should be at or below values recorded during the screening period.

If pre-dose QTcF is 450-469 msec in patients with and without pre-existing BBB and/or pacemaker, APR-246 may be administered, and additional triplicate ECG should be performed at the EOI (6 hours after start of infusion, ± 30 min).

If post-dose ECG shows a significant change in QTcF, defined as either: a) increase >60 msec from baseline (or pre-dose), or b) increase to an absolute value ≥ 501 msec, i.e. consistent with NCI CTCAE Grade 3 QTc prolongation, QTc prolongation must be confirmed by a manual assessment of the ECG, and using Fridericia's correction ($QTcF = QT/RR^{0.33}$). If confirmed, the therapy should be interrupted until a cause (electrolyte disorders or an effect of a concomitant medication) has been identified and addressed, and QTcF has returned to <470 msec. If all other causes for clinically significant QT interval prolongation are excluded, APR-246 must be permanently discontinued. If QTcF is unchanged or there is no significant change, additional ECG is not required during that cycle.

If repeated QTcF measurements show a stable QTcF <450 msec, or if QTcF remains stable within the interval of 450-469 msec with no significant change at the EOI during several cycles of treatment, reducing the number of ECGs performed in the study may be discussed with the Medical Monitor.

If a patient starts treatment with another medication known to prolong QT interval at any time during the study therapy, an additional pre- and post-dose (6 hours after start of infusion, ± 30 min) ECG should be performed on the next treatment day.

6.3.2 Management of CNS Adverse Events

If a patient reports any clinical AE of any grade during the administration period of APR-246 that could be considered to originate from the CNS (e.g. dizziness, vertigo, nausea) then the patient will be given a rescue medication as per the institutional standard of care.

Dose modifications of APR-246 have been successfully used to manage potential CNS effects occurring during the infusion (Table 4). For any clinical AE Grade ≥ 3 , the infusion of APR-246 should immediately be stopped, and if all symptoms resolve to CTCAE \leq Grade 1 within 2 hours, the infusion of APR-246 may be resumed at the same infusion rate. If the same symptoms do occur or increase in severity during re-challenge the infusion of APR-246 should be stopped.

If the event lasts longer than 2 hours, then the APR-246 infusion should be discontinued for that day, the remaining drug should be discarded.

Table 4. Management of CNS Adverse Events (Dizziness, Dyskinesia and Ataxia)

Worst toxicity	Dose Modifications for APR-246
Grade 1	Maintain dose level
Grade 2	If resolved to \leq Grade 1 with medical therapy, continue same dose level If not resolved despite treatment interruption and maximal medical therapy, stop infusion and \downarrow 1 dose level for subsequent dose
Grade \geq 3	Stop infusion and give medical therapy. If resolved (to \leq Grade 1) with medical therapy, infusion may continue at the Investigator's discretion. \downarrow 1 dose level for subsequent dose
Grade 4	Permanently discontinue patient from APR-246.

In prior studies, prochlorperazine 10 mg orally tid (three times daily) has been reported to be an effective treatment that may also be used prophylactically. When prochlorperazine is used prophylactically, start the day prior to the Day 1 and continue 10 mg tid to day 4 (as needed). The US label for prochlorperazine does not list QT interval prolongation as a known risk associated with use of this drug.

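### Section 6.3.2 lets the APR-246 infusion resume after a resolved Grade 4 CNS event, while its own Table 4 requires permanent discontinuation

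*Combined protocol and SAP*

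**What the plan says.** All the relevant wording is in Section 6.3.2, in the running text and in Table 4.

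- **Scope of the text.** The section opens with any event during the infusion "that could be considered to originate from the CNS (e.g. dizziness, vertigo, nausea").
- **Text, event resolves.** For any clinical adverse event of Grade 3 or higher the infusion is stopped at once. If all symptoms return to Grade 1 or less within 2 hours, "the infusion of APR-246 may be resumed at the same infusion rate". If the same symptoms recur or worsen on re-challenge, it is stopped.
- **Text, event lasts more than 2 hours.** The instruction is "then the APR-246 infusion should be discontinued for that day, the remaining drug should be discarded".
- **Table 4, scope and row choice.** The title is "Management of CNS Adverse Events (Dizziness, Dyskinesia and Ataxia"), and rows are chosen by "Worst toxicity".
- **Table 4, row Grade ≥3.** Stop and treat. If the event resolves to Grade 1 or less "with medical therapy, infusion may continue at the" Investigator's discretion, and the subsequent dose drops by one level.
- **Table 4, row Grade 4.** "Permanently discontinue patient from APR-246".

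The text cites Table 4 in the sentence before the stopping rule, but it does not say which prevails if they differ.

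**The concern.** Grade ≥3 includes Grade 4. Read literally, a Grade 4 event of a type named in the table's title, once resolved, meets two written permissions to go on and one absolute bar. The permissions are the resumption sentence and the Table 4 row labelled Grade ≥3. The bar is the Grade 4 row.

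What is at stake is patient safety and uniform handling across sites. These rules are applied at the infusion chair. A site that works from the prose could restart APR-246 in a patient for whom the protocol's own table ends the drug. Another site, working from the table, would stop permanently.

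**Working it through.** No figure in the plan depends on this point, so there is nothing to compute. The check sets the instructions side by side for dizziness, dyskinesia and ataxia, the events that both the text and the table cover.

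| Event | Running text | Table 4 row Grade ≥3 | Table 4 row Grade 4 | Result |
|---|---|---|---|---|
| Grade 3, resolved to Grade ≤1 within 2 h | May resume, same rate | May continue; next dose one level lower | Does not apply | Compatible: the text governs this infusion, the table adds the next dose |
| Grade 3, longer than 2 h | Stop for that day | Next dose one level lower | Does not apply | Compatible if the text's 2-hour limit governs the current infusion |
| Grade 4, resolved to Grade ≤1 within 2 h | May resume, same rate | May continue, if the label is read literally | Permanent stop | **Direct conflict** |
| Grade 4, longer than 2 h | Stop for that day; silent on later doses | Overlaps, if the label is read literally | Permanent stop | The text omits the bar but does not contradict it |

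**Within the table.** Rows are selected by worst toxicity, and Grade 4 has its own row with a different action. The sensible reading is that the row above was meant to say Grade 3. That is an inference, but a strong one: with a Grade 4 row directly below, a label of Grade ≥3 makes the two rows overlap.

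**Between text and table.** Two sentences of the text set an outcome by the 2-hour limit: resume, or discontinue for that day. Neither has a Grade 4 exception. Correcting the row label alone would therefore leave the conflict with the prose.

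**Elsewhere in the protocol.** No other section resolves the conflict:

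- Section 6.1.1 allows a dose reduction for intolerable toxicity.
- Section 6.2 calls for dosing to be delayed for related events above Grade 2. It lets dosing restart, at the Investigator's discretion, at Grade 2 or less, with no Grade 4 exception.
- Section 5.6.1 makes discontinuation mandatory only once the Investigator judges the risk unacceptable.
- Section 6.1.4 defines which events count as DLTs. Its CNS criterion requires failure to resolve to Grade 1 or less within 7 days, so an event that resolves in 2 hours does not meet it.

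**After the fix.** With the row relabelled Grade 3 and a Grade 4 exception in the text, each Grade 4 case in the table above has one outcome, permanent discontinuation. The two Grade 3 cases are unchanged.

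**The case against.** The strongest reply is that the Grade 4 rule is present, mandatory and easy to find. It has its own row in a table that the same paragraph cites, and the resumption sentence is only permissive. A careful reader would let the specific row override the general wording. The text and table can also largely be read together, with the text handling the infusion in progress and the table adding what happens to later doses. Sections 5.6.1 and 6.2 make re-dosing after so severe an event less likely in practice.

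Much of this stands. The permanent stop is very probably what the sponsor intends, and the investigator's duties reduce the risk. It does not remove the conflict in the third row of the comparison, where the text permits the current infusion to restart and the table ends the drug. A safety stop should not depend on an unstated rule about which wording prevails.

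A reader might go further and infer that stopping for that day authorises dosing on the next day after a longer Grade 4 event. The documents do not support this: the sentence is silent on later doses, and Table 4 settles them for the events it covers.

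A reader might also infer that the Grade 4 bar is meant for every CNS event. The table's title names three event types, while the text also mentions vertigo and nausea. Whether the bar extends further is a question for the sponsor, not a demonstrated error.

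**Conclusion.** The inconsistency is real and should be corrected. It is a patient-safety matter of limited extent: the direct conflict is confined to Grade 4 dizziness, dyskinesia or ataxia during the infusion that resolves to Grade 1 or less within 2 hours. For longer events the text only fails to carry over the permanent bar.

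The conclusion assumes that Grade 4 can be assigned to these events. CTCAE version 5.0 is not in the documents, so this cannot be checked here. The visible text gives no frequency for such events, so the number of patients affected cannot be estimated and the event should not be called rare or common.

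Three further inferences are tempting and are not supported:

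- **That safety reporting comes too late because 24 hours exceeds 2 hours.** The 2 hours limits the time for symptoms to resolve; it is not a deadline for restarting. Section 8.1.2.6 requires immediate SAE notice, with 24 hours as the outer limit. The two are not comparable.
- **That the absence of DLTs in the lead-in shows how often this arises.** Under the CNS criterion, a Grade 4 event that resolved quickly need not have been a DLT.
- **That trial conclusions are affected.** The RP2D, the sample size and the efficacy analyses do not depend on which instruction a site follows here.

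**What to change.** Make two edits in Section 6.3.2:

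1. In Table 4, change the row label Grade ≥3 to Grade 3.
2. After the resumption sentence and the sentence on events longer than 2 hours, add an exception along these lines: *A Grade 4 event covered by Table 4 ends APR-246 treatment permanently, whether or not it resolves.*

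At the same time, the sponsor should confirm whether the Grade 4 bar is meant to reach CNS events outside the table's title, such as vertigo, and adjust the title if so.

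The cost is one label and one clause in the next amendment, with no change to the design, sample size or analysis.
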